the 90-day FU to assess YMSM's satisfaction with the intervention, including the content, site layout and design, and general satisfaction. These domains are assessed on a 4-point response scale with individually specified anchors. The CSQ-8 has demonstrated high internal consistency across a large number of studies⁹⁵. The SEF and CSQ will take approximately 10 minutes to complete. We will also track users' actions in the intervention as process evaluation data. These data will include the number of times that they visited the site, their geographic location and the website from which they linked to our site, time spent in each session, number of times a user returns to a session, and which interactive features were "clicked on" during sessions.

Behavioral Assessments. The web surveys will be programmed to minimize out-of-range or inconsistent responses. Data exports will be automated into SPSS. The survey will be designed using best practices to encourage completion⁹⁶. Planned domains are listed below and may be refined based on the intervention content developed and YAB feedback. Based on our prior success in recruiting YMSM to complete online surveys, we will use best practices (e.g., surveys are dynamic and take less than 30 minutes to complete) to reduce participant burden. We have used all measures previously; scales have strong psychometric properties (i.e., adequate factor structure and $\alpha > .65$). Table 3 documents when domains will be assessed.

Table 3. Assessment Summary Table	BL	FU1	FU2	FU3
Sociodemographic Information				
Demographic data (e.g., race, sexuality)	X			
Social media use	X			
Changes in relationship, housing, work	X	X	X	X
Outcome indicators				
Sexual behavior	X	X	X	X
Recent HIV/STI test	X	X	X	X
Substance use	X	X	X	X
Predictors of Behavior Change				
TPB Constructs	X	X	X	X
Affective Motivations	X	X	X	X
Partner-seeking behaviors	X	X	X	X
Psychological Risk Correlates	X	X	X	X

information.

Outcome indicators: Consistent with our model, we have 3 primary risk reduction outcomes: increased consistent condom use across partner types (continuous), reduced number of UAI partners and occasions (continuous), and increased HIV/STI testing rates (dichotomous). We detail their assessment below:

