Sexual behaviors will be assessed using the Sexual Practices Assessment Schedule⁹⁷ used in previous online studies with YMSM to explore the number of occasions of different sexual acts (oral, anal; receptive, insertive) with different partner types. SPAS allows us to estimate the number of UAI partners and occasions across partner types, as well as the proportion of instances when condoms were not used^{70,98,99}. SPAS also ascertains YMSM's use of condoms during the past 30 days (1=Never/5=Always) and their HIV status disclosure practices with each partner. SPAS measures behaviors with male and female partners, respectively.

HIV/STI Testing Behaviors. We will ask YMSM to indicate the date of their more recent HIV and STI tests. Subsequently, we will ask participants to note if they have ever been medically diagnosed as having one or more STIs, the date of their most recent STI test if available, and whether a medical provider had previously diagnosed them with a STI. At each FU, we will ask participants whether they have gone to get tested for HIV and/or STIs, respectively. If tested, participants were asked to indicate what tests they received and whether they had been medically diagnosed as having HIV or STI. At FU, we will ask YMSM whether they have had any changes in their HIV status. Newly diagnosed cases will be asked if they were linked to care.

Psychosocial indicators of behavior change. To measure *TPB constructs*, we will measure YMSM's attitudes, subjective norms, self-efficacy using previously tested scales with MSM^{7,100,101}. We will use existing items measuring condom use intentions with different partner types, and self-efficacy to negotiate condoms with different partner types¹⁰². Descriptive and personal norms will be measured separately for different partner types (1=Strongly Disagree/Strongly Agree)¹⁰⁰. We will measure these constructs at baseline and FUs.

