Estimation of parameters for a subsequent R01. Consistent with the R34 mechanism, the primary role of this pilot RCT is to ensure that the critical parameters required to plan a large trial are estimated as informatively as possible. Certain principles then follow: (1) If alterations are necessary to address measurement or performance problems, these will be permitted in an effort to establish optimal procedures and design parameters before a future trial, precisely so that no changes in protocol will be required during a future trial; and, (2) Estimation of critical design parameters with point and confidence interval estimates will be considered highly important, as large sample sizes are not required to locate these parameters adequately when planning for a subsequent trial. As a result, we are not powered to estimate small effect sizes or carry out sophisticated statistical analyses; rather, we seek to estimate key study parameters with sample means and proportions together with two-sided 95% confidence intervals, and test the primary null hypotheses at the

traditional two-sided level $\alpha=.05$.

To test for intervention effects over time with pilot RCT data, we will use the general framework of generalized

linear mixed models (GLMM) to model the longitudinal outcome trajectories¹¹⁰⁻¹¹². Note that some of our outcomes

are binary, some count and some continuous traits and thus need to be treated differently. The general form of the GLMM will be $(\mu_{ij}) = \beta_{0i} + \beta_{cov} Covariates_{ij} + \beta_{visit} Visit_j +$

Table 4. Detectable Effect (.80 power, alpha=.05)	N = 140	N = 160	N = 180
Continuous Outcomes			
Within-subject correlation (rho=.4)	.39	.35	.33
Within-subject correlation (rho=.5)	.41	.38	.35
Within-subject correlation (rho=.6)	.44	.40	.37
Binary Outcomes (p(NTHP)=.40)			
Within-subject correlation (rho=.4)	2.19	2.04	1.93
Within-subject correlation (rho=.5)	2.31	2.14	2.02
Within-subject correlation (rho=.6)	2.43	2.24	2.11

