$\beta_{Trt} Trt_i + \beta_{Trt \times visit} rt_i \times Visit_j$, where μ_{ij} is the mean response corresponding to subject *i* on visit *j* (*baseline and three follow-ups*), *g* denotes the link function (identity for continuous outcome, logit for binary outcome and natural log for count outcomes); $Trt_i = 1$ if the *i*-th subject is in the MEET-ME group and 0 if the *i*-th subject is in the NTHP group. The variable Visit can be coded in different ways depending upon how one wants to model the effect of time on the mean response. For example, for characterizing only pre vs. post effect Visit can be coded as a binary indicator with 0 representing baseline and 1 representing post-randomization; Assuming a linear time trend, Visit can be coded as 0, 1, 2, 3, or it can be simply coded as a categorical variable representing the distinct effect of each visit compared to the baseline. The interaction coefficients $\beta_{Trt \times Visit}$ are of interest here, measuring the difference in the rate of change in outcome across the two treatment groups at each visit. If the baseline outcome measure is included as a part of the covariates on the right hand side of the

NCT02842060

above equation, then we only have three repeated measures on the left hand side of the model ($j=1,2,3$) and we can look at average treatment effect across visits without including the $Trt \times Visit$ interaction term. In this particular case, the GLMM analysis with continuous outcome will be equivalent to a repeated measures analysis of covariance after adjusting for baseline values. The subject-specific random intercepts β_{0i} are assumed to be normally distributed with a common variance and they account for within-person correlation. We will also explore if we need a subject specific random-slope corresponding to visit in the above model. Maximum likelihood estimation will be used for fixed effect parameters. Models will be compared according to information criterion like AIC, BIC. For some binary outcomes like STI/HTV testing, we will perform an aggregate analysis after collapsing across the repeated measures using simple logistic regression comparing whether the probability of having tested at least once over the entire FU period is different across treatment groups, after adjusting for baseline values. To ensure robustness, we will also apply an exchangeable working correlation structure to its corresponding generalized estimating equation (GEE) model.

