Power for primary analysis: As shown in Table 4, we will have 80% power to detect a medium intervention effect (Cohen's $d > .35$) at $\alpha=.05$ in a continuous measure using a repeated measures group design (N=180) with 4 observations (baseline + 3 FUs) when the standard deviation is 1 and the correlation between observations on the same subject (ρ) is 0.6. For dichotomous outcomes, we estimate 80% power at $\alpha=.05$ to detect an odds ratio of 2.11 or greater assuming that the proportion for the intervention condition is .58 and the attention-control condition is .40, with ρ also being .60. We note that there is some controversy regarding the use of "pilot data" to estimate the actual effect size, as specified by Kraemer et al.¹¹³. We agree with their view that clinically meaningful effect sizes should be decided based on extrinsic, clinical judgment grounds, and not based on the pilot data which are too few, typically, to obtain reliable conclusions. However, we can use these data to rule out unusually large or small effects through standard 95% confidence interval procedures. Thus, we will confirm that extrinsic effect sizes are contained within our confidence intervals¹¹³ and use these Even with 20% attrition, we will have preliminary effects with adequate error margins to inform the subsequent trial.

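### Table 4's binary detectable odds ratios rest on four averaged observations per man and are not the power of the collapsed ever-tested analysis named for HIV/STI testing

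*Combined protocol and SAP*

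**What the plan says.** - **Outcome.** Outcome indicators lists the primary outcomes. Only one carries a binary label: "increased HIV/STI testing rates (dichotomous". Under HIV/STI Testing Behaviors it is collected visit by visit: "At each FU, we will ask participants whether they have gone to get tested for HIV and/or STIs, respectively". At baseline the item is the date of the latest test.
- **Analysis.** Data Analyses sets out a generalized linear mixed model (GLMM), with a logit link for binary outcomes. If baseline enters as a covariate, "then we only have three repeated measures on the left hand side of the model". For some binary outcomes, with testing as the example, the repeated answers are collapsed and a simple logistic regression compares "whether the probability of having tested at least once over the entire FU period is different across treatment groups, after adjusting for baseline values". A GEE is added for robustness.
- **Power.** The table is headed "Table 4. Detectable Effect (.80 power, alpha=.05" and its lower block "Binary Outcomes (p(NTHP)=.40". The N=180 column gives 1.93, 2.02 and 2.11 for rho .4, .5 and .6. Power for primary analysis claims 80% power "to detect an odds ratio of 2.11 or greater assuming that the proportion for the intervention condition is .58", against .40 in the control arm with rho .60. Its sentence on continuous outcomes describes the design as "using a repeated measures group design (N=180) with 4 observations (baseline + 3 FUs".

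**The concern.** A within-subject rho and a gain from repeated observations belong to a model with several outcomes per man. The collapsed regression has one outcome per man. It can gain from the baseline covariate, but not by averaging visits. The tabled odds ratios therefore cannot be carried over to it, and nothing else in the plan gives its sensitivity.

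The direction also differs. In Table 4 a higher rho makes the detectable odds ratio worse (1.93 to 2.11). In the collapsed model a higher correlation with baseline makes it better. The entries that look most favourable in Table 4 are therefore the ones furthest from 80% under the named analysis.

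The figures stand under a heading about the primary analysis, and the plan tests its primary null hypotheses at two-sided .05. A colleague planning the larger trial could take them as the sensitivity of the testing comparison.

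**Working it through.** **Inputs from the documents.** Two-sided alpha .05; 120 MEET-ME and 60 control (Phase 3, Recruitment); control proportion .40 and the three OR/rho pairings (Table 4); attrition 20% (Phase 3), which leaves 0.8 × 120 = 96 and 0.8 × 60 = 48.

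**Assumptions, because the documents are silent.** .40 is the ever-tested control rate (the per-visit reading is in step 4); baseline prevalence of testing is .40; the baseline correlation is varied.

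**Formula.** p1 = .40; p2 = odds/(1 + odds) with odds = OR × .40/.60; p̄ = (60p1 + 120p2)/180.

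Power = Φ{[(p2 − p1) − 1.96·s0]/s1}, with s0² = F·p̄(1 − p̄)(1/60 + 1/120) and s1² = F·[p1(1 − p1)/60 + p2(1 − p2)/120]. F is the variance factor of the design.

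**Step 1. Reproduce Table 4.** Averaging four exchangeable observations gives F = (1 + 3rho)/4 = .55/.625/.70. For OR 2.11: p2 = .5845, p̄ = .5230, s0 = .0661, s1 = .0649. Then (.1845 − .1295)/.0649 = .847, and power is .80.

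| Observations averaged | Solved OR, rho .4 | rho .5 | rho .6 |
|---|---|---|---|
| Four, F = (1 + 3rho)/4 | 1.936 | 2.022 | 2.107 |
| Three, F = (1 + 2rho)/3 | 1.994 | 2.070 | 2.145 |
| Table 4, N=180 | 1.93 | 2.02 | 2.11 |

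Only four observations fit. The continuous rows at N=180 (.33/.35/.37) also reproduce with four.

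**Step 2. Collapsed model, no credit for baseline.** One indicator per man, so F = 1. For OR 2.11: s0 = .0790, s1 = .0776, (.1845 − .1548)/.0776 = .383, power .65. The three pairings give .54/.60/.65. The OR detectable with 80% power is 2.44.

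**Step 3. Collapsed model, baseline correlation set equal to rho.** As an approximation F = 1 − r², that is .84/.75/.64. The formula gives .61/.72/.84. Simulated logistic regressions on treatment and baseline (Wald test, 40,000 runs) give .61/.72/.83. Setting the formula to 80% at OR 2.11 gives r = .545; simulated power at r = 0/.4/.5/.55/.6 is .65/.72/.77/.80/.83. Detectable ORs by simulation at r = .4/.5/.6 are about 2.27/2.17/2.05.

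With 96:48, simulation gives .51/.62/.74 (formula .52/.62/.75).

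**Step 4. Sensitivity.**
- *.40 and the tabled ORs read as per-visit, exchangeable rho.* The any-of-three indicator gives .60/.64/.67 without baseline credit and about .67/.74/.82 with it (all 180 men).
- *Baseline prevalence .40 to .60.* With baseline credit and all 180 men, power across both readings of .40 is 61–69%, 72–78% and 82–89%.
- *Lower baseline prevalence.* At .30, a correlation of .6 with a treated rate of .585 is impossible: the implied conditional probability is .5845 + .6 × √(.5845 × .4155) × √(.7/.3) = 1.04. The favourable case is not available everywhere.

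**Step 5. Repeated-visit alternative.** For three follow-ups with baseline as covariate, an approximate F is (1 + 2rho)/3 − rho² = .440/.417/.373. Power at the tabled pairings is then about .88/.93/.97, so the tabled ORs would be conservative for that model.

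**Limit of the reproduction.** The N=160 and N=140 columns fit splits of 110:50 and 100:40, not 2:1. Nothing here relies on them.

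**The case against.** The strongest objection is that the plan never says the collapsed regression is primary. The GLMM with a logit link is the general framework, the collapsed model is an addition for some binary outcomes, and the power sentence speaks of dichotomous outcomes in general. A reader might infer that the plan contradicts its own primary analysis. The documents do not support that: the primary model for testing is left open. What remains is that the only analysis tied by name to testing has no power figure. Averaging four observations does not rescue the table either. It puts the pre-randomisation value into the treatment contrast, which is neither the visit-interaction model nor the baseline-as-covariate model that Data Analyses describes.

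A second objection is that this is a pilot. The plan disclaims power for small effects, puts estimation with confidence intervals first, and takes effect sizes for the larger trial from clinical judgment. That stands, and it limits the consequence. It does not remove a specific 80% claim placed under a primary-analysis heading.

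Third, baseline adjustment could restore the headline figure. It could, but the plan gives rho only for observations on the same man. It gives no correlation between baseline testing and the collapsed indicator, and defines no binary baseline variable from the date of the last test.

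**Conclusion.** The point holds as a mismatch between the power statement and the named analysis. At N=180 the rho .4 and .5 entries miss 80% for the collapsed model in every version tried. The OR 2.11/rho .6 entry reaches 80% only if the baseline correlation is about .55 or more and all 180 men are analysed. Without baseline credit it has about 65%, and with 20% attrition and correlation .6 about 74%.

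Two stronger readings are tempting. One is that the testing comparison cannot reach 80% at the tabled effects. That does not follow: a high enough baseline correlation, or the repeated-visit model with baseline as covariate, would reach it. The other is that Table 4 is miscalculated. The N=180 arithmetic is right for four averaged observations; the fault is that it describes a different analysis.

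The figures rest on .40 as the ever-tested control rate, baseline prevalence .40 and a Wald test. Severity is minor to moderate.

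**What to change.** State which model is primary for HIV/STI testing, then do one of the following.

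1. **Collapsed model.** Replace the binary rows of Table 4 and the OR 2.11 sentence with figures for that model. Give the assumed ever-tested control rate, how the baseline testing variable is derived, its assumed correlation with the collapsed indicator, and the number of men analysed. At N=180 with a control rate of .40, the detectable OR is about 2.44 without baseline credit, and about 2.27/2.17/2.05 at correlation .4/.5/.6. Add the 96:48 case.
2. **Repeated-visit model.** Say that the binary figures apply only to that model and not to the collapsed analysis, state that .40 and .58 are per-visit proportions, and recompute for three follow-ups with baseline as covariate. The approximate factor in step 5 suggests the tabled ORs would prove conservative.

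The cost is wording and a few table cells. Option 1 makes the stated sensitivity conditional and, at lower correlations, less favourable. Option 2 makes the estimand a per-visit odds ratio instead of ever tested, which is a choice for the study team. Neither changes the design or the sample size.

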Psychological risk correlates. We will measure *depression*, *anxiety*, and *loneliness* symptoms as markers of psychological distress. Depression and anxiety symptoms in the past week will be measured using the Brief Symptom Inventory¹⁰⁵. Both scales include 6 items rated on a 5-point scale (1=never, 5 = very often), respectively. We will use the UCLA Loneliness scale¹⁰⁶ to measure feelings of loneliness (1=Never;4=Often). We will also measure *self-esteem* using Rosenberg’s scale¹⁰⁷, a 10-item measure using a 5-point scale. We will measure *internalized homophobia*¹⁰⁸ with 12 items measured on a 4-point scale (0=Strongly disagree; 3=Strongly agree). Finally, we will measure *sexuality-related stressors* using a 9-item scale (0=never/4=3+ times) with strong reliability¹⁰⁹ assessing the frequency of discriminatory events (e.g., verbal insults) due to someone knowing/assuming YMSM were gay/bisexual.

Data Analyses. Prior to conducting our multivariate analyses, we will examine study variables using descriptive statistics and test for differences across demographic characteristics (e.g., race/ethnicity, age, education) using t-tests, ANOVAs, and Chi-squares, as appropriate. As participants will be randomized to the two treatment groups, systematic baseline differences are not expected; however, in the event that some parameters differ across conditions at baseline, they will be included as covariates in subsequent multivariate models. We will calculate descriptive summary statistics corresponding to the study variables at each visit to understand any temporal patterns, as well as compare the two treatment groups in terms of average change from baseline after intervention (averaged across all three FU times).

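### The power statement gives d > .35 for N=180 at a within-subject correlation of .6, but the Table 4 cell it cites is .37

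*Combined protocol and SAP*

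**What the plan says.** The paragraph headed Power for primary analysis opens by citing Table 4. For continuous outcomes it states "we will have 80% power to detect a medium intervention effect (Cohen's $d > .35", and it fixes the conditions: N=180, baseline plus three follow-ups, standard deviation 1, alpha .05 and a within-subject correlation of .6.

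For dichotomous outcomes the next sentence claims the same power "to detect an odds ratio of 2.11 or greater", "assuming that the proportion for the intervention condition is .58 and the attention-control condition is .40". It adds that the correlation is again .60.

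The cited table, under Estimation of parameters for a subsequent R01, is titled "Table 4. Detectable Effect (.80 power, alpha=.05" and closed with a bracket. It has columns for N=140, 160 and 180, and rows for correlations of .4, .5 and .6 within each outcome type.

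**The concern.** The sentence names its source and all its conditions, so it can be checked against one cell. The continuous row labelled "Within-subject correlation (rho=.6" reads .44, .40 and .37 across the three sample sizes. At N=180 the detectable effect is therefore .37, not .35.

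What is at stake is the reliability of a quoted design figure. The plan says the main role of the pilot is to supply parameters for planning a larger trial. A reader who takes the effect size and the correlation from the prose carries forward a pair that the plan's own table contradicts.

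**Working it through.** **1. Text against table (no formula needed).** Table 4, N=180 column:

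| Within-subject correlation | Continuous (d) | Binary (odds ratio) |
|---|---|---|
| .4 | .33 | 1.93 |
| .5 | .35 | 2.02 |
| .6 | .37 | 2.11 |

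The text gives d = .35 and an odds ratio of 2.11, both for a correlation of .6. The odds ratio matches the .6 row. The effect size equals the .5 row.

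**2. The binary sentence does rest on the .6 row.** The control proportion of .40 has odds .40/.60 = .6667.

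- Odds ratio 2.11: .6667 × 2.11 = 1.4067, and 1.4067/2.4067 = .584. This rounds to the stated .58.
- Odds ratio 2.02: .6667 × 2.02 = 1.3467, and 1.3467/2.3467 = .574. This rounds to .57.

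**3. Is the printed .37 itself sound?** The plan does not state the formula behind Table 4, so this step is an inference. Inputs: the plan's "traditional two-sided level $\alpha=.05", 80% power, 120 and 60 participants, standard deviation 1. Suppose the two groups are compared on the mean of four equally correlated observations:

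- detectable d = (1.960 + 0.842) × √{[(1 + 3ρ)/4] × (1/120 + 1/60)}, where 1/120 + 1/60 = .025
- ρ = .4: 2.802 × √(.55 × .025) = .3285 (printed .33)
- ρ = .5: 2.802 × √(.625 × .025) = .3502 (printed .35)
- ρ = .6: 2.802 × √(.70 × .025) = .3706 (printed .37)

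The whole N=180 continuous column is reproduced, which supports the table cell over the prose. With an exact 2:1 split, the formula matches only one of the three N=160 cells and none at N=140, so four of nine in all. With splits of 110:50 and 100:40 it matches all nine, but the plan does not state those splits.

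**4. Scale of the discrepancy.** Power at d = .35, ρ = .6 and 120:60, as the normal probability below d/SE − 1.960, assuming a constant difference d over the observations compared after randomisation (over all four for the first row):

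| Comparison | SE | Power |
|---|---|---|
| Mean of four observations (inferred basis of Table 4) | √(.70 × .025) = .1323 | 75.4% |
| Mean follow-up minus baseline | √{[(1+2ρ)/3 + 1 − 2ρ] × .025} = √(.5333 × .025) = .1155 | 85.8% |
| Baseline-adjusted mean of three follow-ups | √{[(1+2ρ)/3 − ρ²] × .025} = √(.3733 × .025) = .0966 | 95.2% |

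The second row corresponds to the comparison of "average change from baseline after intervention (averaged across all three FU times" in Data Analyses. The third corresponds to the model with baseline as a covariate, of which the plan says "then we only have three repeated measures on the left hand side of the model". Data Analyses describes no comparison of the four-observation average.

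**The case against.** The strongest reply is that almost nothing follows from the error. The correct value is printed in the table the sentence cites, the gap is .02, and the plan says repeatedly that the pilot is not powered for small effects. It also says that effect sizes for the larger trial should be set on clinical grounds and not from pilot data. For the two analyses the plan does describe, power at d = .35 is above 80% (85.8% and 95.2%), so the sentence is not optimistic about them. All of this stands. It limits the point to a correction of the text, and the 75.4% must not be read as a shortfall in the trial.

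A second reply is that the source of .35 is unknown. It equals the .5 cell at N=180, but it is also the N=160 cell for a correlation of .4. The formula in step 3 with equal arms of 90 gives .349 at a correlation of .6, so it could be left over from a 1:1 calculation. This also stands: the documents show that .35 is not the cited cell, not how it got there. The 1:1 explanation would not make the sentence right, because the design is 2:1 and the N=180 column agrees with 120:60.

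A third reply is that an effect above .35 includes .37. This does not help. The sentence offers .35 as the threshold for 80% power, and by the table an effect between .35 and .37 passes that threshold without reaching the stated power. The binary sentence quotes its cell value exactly.

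**Conclusion.** The concern holds as a minor error. The prose states .35 where the table it cites states .37, for N=180 and a correlation of .6. This conclusion rests only on the two places in the document. The rows and columns of the continuous block are complete and ordered, rising with the correlation and falling with N, so there is no sign that the cell was displaced in conversion.

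The power percentages give scale only. They depend on an inferred formula or on the simple variance expressions shown, with equal correlation between all visits and no attrition. The mismatch alters no sample size, analysis or decision rule.

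**What to change.** In Power for primary analysis, replace d > .35 with d ≥ .37 and leave the correlation at .6. Both headline figures then come from the .6 rows of Table 4 at N=180. Changing the correlation to .5 instead would be the poorer repair, because the next sentence says that .60 applies to the binary figure as well. The cost is one number in one sentence, with no effect on design, analysis or conduct.

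### Table 4's 80% power does not belong to any analysis the plan describes; at its own effect sizes the planned contrasts have 44% to 97% power

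*Combined protocol and SAP*

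**What the plan says.** Under *Power for primary analysis*, the plan claims 80% power for a medium effect on a continuous outcome "using a repeated measures group design (N=180) with 4 observations (baseline + 3 FUs) when the standard deviation is 1" and a within-person correlation (rho) of .6. It claims the same power for an odds ratio of 2.11 on a binary outcome, with proportions of .58 and .40. The supporting table is headed "Table 4. Detectable Effect (.80 power, alpha=.05)". For N=180 and rho .4/.5/.6 it lists d of .33/.35/.37 and odds ratios of 1.93/2.02/2.11.

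The comparisons that will be made are described in *Data Analyses* and in the mixed-model text that follows *Estimation of parameters for a subsequent R01*:

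- Descriptively, the plan will "compare the two treatment groups in terms of average change from baseline after intervention (averaged across all three FU times)".
- In the mixed model, the treatment-by-visit coefficients are of interest, "measuring the difference in the rate of change in outcome across the two treatment groups at each visit". The coding is left open: "The variable Visit can be coded in different ways depending upon how one wants to model the effect of time on the mean response". Pre/post, linear and categorical codings are all offered.
- If baseline is a covariate, "then we only have three repeated measures on the left hand side of the model", and the average treatment effect over the follow-ups is examined.
- For some binary outcomes such as HIV/STI testing, a collapsed logistic regression asks whether "the probability of having tested at least once over the entire FU period is different across treatment groups".

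None of these is named as primary. On baseline, the plan says "systematic baseline differences are not expected".

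**The concern.** A power figure belongs to one contrast. Counting baseline as one of four observations in a group comparison treats it as carrying treatment effect, which randomisation rules out. The planned contrasts either subtract baseline or adjust for it, so they have different variances and respond to the correlation in the opposite direction.

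If Table 4 was computed for some other contrast, a reader cannot tell what effect the pilot can detect. The stated 80% could be too high or too low, depending on which contrast is eventually used.

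**Working it through.** **Inputs.** Two-sided alpha .05, 80% power and the detectable effects come from Table 4 and the text before it. SD 1, rho .6 and the binary proportions come from *Power for primary analysis*. The 120:60 split comes from the Phase 3 *Recruitment* section. My assumptions are exchangeable correlation, no effect at baseline and, at first, no attrition.

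**Formulas.** With 1/120 + 1/60 = .025, SE = √(V × .025). Detectable d = (1.96 + 0.8416) × SE / k. Power = Φ(k·d/SE − 1.96). V is the variance factor of the contrast and k is the share of d that it carries.

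**Step 1: reproduce the plan's figures.** For the mean of four observations, V = (1+3rho)/4 = .55/.625/.70 and SE = .1173/.1250/.1323. With k=1, d = .329/.350/.371, which matches .33/.35/.37. The unadjusted mean of three follow-ups, V = (1+2rho)/3, gives .343/.362/.379 and matches no cell.

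For the odds ratios, the same factor with pooled variance under the null and unpooled under the alternative gives 1.94/2.02/2.11 against 1.93/2.02/2.11.

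The N=140 and N=160 continuous cells fit this formula only with splits near 100:40 (.389/.414/.438 against .39/.41/.44) and 110:50 (.354/.378/.400 against .35/.38/.40). No section gives those splits. At 2:1 the formula gives .37/.40/.42 and .35/.37/.39. The binary cells in those two columns come within about .015 but do not all match.

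**Step 2: the planned continuous contrasts, 120:60, the same d at all three follow-ups.**

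| Contrast | V | k | Detectable d, rho .4/.5/.6 | Power at Table 4's d |
|---|---|---|---|---|
| Linear treatment × visit | 1.8(1−rho) | 0.9 | .51/.47/.42 | 44/56/70% |
| Visit-specific interaction | 2(1−rho) | 1 | .49/.44/.40 | 48/60/74% |
| Pre/post, or average change | 4(1−rho)/3 | 1 | .40/.36/.32 | 65/77/89% |
| Baseline-adjusted, three follow-ups | (1+2rho)/3 − rho² | 1 | .29/.29/.27 | 88/93/97% |

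Example at rho .6, visit-specific: SE = √(.8 × .025) = .1414, and power = Φ(.37/.1414 − 1.96) = Φ(.656) = 74%. A joint three-degree-of-freedom interaction test has 48/61/77%. Simulation with 8,000 trials per rho agreed with the four rows to within about 1.5 percentage points.

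No row gives .33/.35/.37. In every row the detectable d falls as rho goes from .4 to .6; in Table 4 it rises.

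**Step 3: the reproduced contrast when the effect starts after baseline.** The four-observation mean then carries k = 0.75. At rho .6, Φ(.2775/.1323 − 1.96) = 55%; over the three rows power is 56/56/55%.

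**Step 4: a different effect shape.** If d accrues linearly to day 90, power at Table 4's d is 52/65/79% for linear coding, 48/60/74% for the day-90 interaction, 34/44/57% for pre/post and 55/63/72% for the baseline-adjusted model. The last two now carry only 2d/3.

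**Step 5: attrition.** The plan projects 20% loss by day 90 but gives no staging. With an assumed cumulative 7/14/20%, a constant d and the mixed model:

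| Contrast | Power at Table 4's d | Detectable d |
|---|---|---|
| Visit-specific at day 90 | 42/53/67% | .52/.48/.43 |
| Pre/post | 62/74/87% | .41/.38/.34 |
| Baseline-adjusted | 84/90/95% | .31/.30/.29 |

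**Step 6: the collapsed binary analysis.** One value per person leaves no repeated-measures correlation to use (V = 1). If the cumulative control proportion is assumed to be .40, the detectable odds ratio at 120:60 before baseline adjustment is about 2.4 (2.41 to 2.48 across four variance forms), not 2.11. If .40 is instead per visit (assumed beta-binomial, rho .6), the cumulative proportions are about .55 and .73, and power is about 68%.

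**Side check.** The text pairs d above .35 with rho .6; Table 4 gives .37 there and .35 at rho .5. At d = .35 and rho .6 the four-observation formula gives 75%.

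**The case against.** This is a pilot. The attention-control description, the Phase 3 introduction and the parameter-estimation section all disclaim power for small effects, and estimation with confidence intervals is its stated main role. That limits the consequence. But the plan also commits to testing its primary null hypotheses at .05 and gives a specific 80% for a medium effect. A disclaimer about small effects does not make that figure right.

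The four-observation formula is inferred, since the plan states none. That stands. The conclusion does not rest on it: the planned contrasts fail to reproduce the N=180 cells, and they move the wrong way with rho, whatever formula was used.

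The 44% is an unfavourable extreme. It is the linear coding at rho .4 with a step effect, and the plan offers that coding under an assumed linear trend. It also belongs to a row that the text sentence does not use. Both points are fair. Table 4 does claim 80% in that row, so the range is valid for the table. At rho .6 it is 70% to 97%, or 74% to 97% without the mismatched linear case, and two planned contrasts exceed 80%.

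The attrition staging and the per-visit binary model are assumptions from outside the documents. They illustrate size and are not needed for the conclusion.

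**Conclusion.** The concern holds. The stated 80% is not a property of any continuous contrast the plan describes. Under exchangeable correlation, SD 1, 120:60, no attrition and a constant post-baseline effect, power at Table 4's own d runs from 44% to 97%. Interaction codings mostly fall below 80%; the exception is pre/post at rho .6, with 89%. The baseline-adjusted model is above 80% throughout. Under linear accrual all the planned contrasts fall below 80%, with a low of 34%.

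The error therefore runs in both directions. It does not undermine N=180, because with a constant effect the baseline-adjusted model detects smaller d than Table 4 states. The pilot can also estimate rho from its own data. This should be fixed, but it is a fault in the power statement and in the unnamed primary contrast, not in the design.

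**What to change.** Name one primary contrast per outcome type from those already in the mixed-model text, with its Visit coding and assumed effect shape. Recompute Table 4 for it, state the arm sizes behind each column, and rewrite the two sentences in *Power for primary analysis* to match, which also removes the .35/.37 conflict. The detectable d values in the working can be used for a constant effect. If linear coding is chosen with accrual to day 90, they are .46/.42/.38.

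If attrition is shown, state the assumed staging. Label any 96:48 figures as a complete-case worst case: .33/.32/.30 baseline-adjusted, .44/.40/.36 pre/post and .54/.50/.44 visit-specific.

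For HIV/STI testing, say whether .40 is a per-visit or a cumulative proportion. If the collapsed regression is primary and .40 is cumulative, give an odds ratio of about 2.4 before baseline adjustment. Any figure for count outcomes needs a mean and dispersion, which the documents do not give, stated as assumptions.

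The cost is one analysis decision per outcome type, one recalculated table and two sentences. Enrolment and data collection are unaffected.
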